## Clinical Investigation Plan

### **COMPLIANCE STATEMENT:**

This clinical investigation will be conducted in accordance with this Clinical Investigation Plan, the Declaration of Helsinki and the applicable regulatory requirements (such as, 21 CFR Part 50, 21 CFR Part 56, 21 CFR Part 812, 21 CFR Part 54, and 21 CFR Part 11 and 45 CFR part 46). The conduct of the clinical investigation will be approved by the Food and Drug Administration (FDA) and the appropriate Institutional Review Board (IRB) of the respective investigational site.

*This confidential document is the property of Abbott and shall not be reproduced, distributed, disclosed or used without the express written consent of Abbott*

## Clinical Investigation Plan

### 1.0 INTRODUCTION

This clinical investigation will be conducted in accordance with this CIP. All investigators involved in the conduct of the clinical investigation will be qualified by education, training, or experience to perform their tasks and all study specific training will be documented appropriately.

### 1.1 **Background and Rationale**

[figure not shown]
#### 1.1.1 **Background**

The Virtual Flow Reserve (VFR) software provides an estimate of Fractional Flow Reserve (FFR) to facilitate the assessment of the hemodynamic significance of coronary lesions imaged by optical coherence tomography (OCT).

*This confidential document is the property of Abbott and shall not be reproduced, distributed, disclosed or used without the express written consent of Abbott*

## Clinical Investigation Plan

### 1.1.2 Rationale for Conducting this Clinical Investigation

FFR has been a useful tool to assess the functional severity of a stenotic lesion in a coronary artery and determine the need for revascularization in many clinical studies (1,2). FFR is the ratio between the pressure distal to the stenosis and the aortic pressure during hyperemia. The predominant advantage of percutaneous coronary intervention (PCI) guidance by coronary physiology is that FFR integrates variables such as luminal narrowing with myocardial perfusion area and collateral flow, leading to a more accurate assessment of myocardial ischemia than coronary angiography alone (1). It has been shown that coronary revascularization can be safely deferred if FFR is above the ischemic threshold of 0.80 (2,3).

The most recent ESC guidelines on myocardial revascularization recommend FFR with the highest degree (Class I, Level of Evidence A) to assess the hemodynamic relevance of intermediate-grade stenosis when evidence of ischemia is not available (4). Pre-PCI FFR has a Class IIa, Level of Evidence B recommendation in Canada, and the US (5). Despite all these recommendations, the adoption rate for FFR remains sub-par, partially due to the use of costly pressure wires and patients' discomfort from the administration of hyperemic agents.

These limitations of FFR may be overcome in part by image-based physiology assessment. For instance, the HeartFlow FFRCT applies computational fluid dynamic (CFD) simulation on CT angiography, which provides a non-invasive coronary fractional flow reserve measurement without a coronary pressure wire or hyperemic agent (6-8). CathWorks FFRangio is derived from routine coronary angiography creating a three-dimensional (3D) reconstruction of the coronary arterial system and estimating the resistance and flow across stenosis (9).

However, FFRCT is limited to a small patient population, given the relatively low penetration of coronary CTA in the US. Additionally, CT imaging technology has significant limitations in the presence of calcified coronary arteries and prior metallic stents (10,11). Furthermore, despite being a non-invasive procedure, both FFRCT and FFRangio may not accurately provide enough detailed vascular morphology compared to intravascular images, which is essential to optimize PCI procedures.

Optical Coherence Tomography (OCT) provides intravascular imaging with high-resolution (10-20  $\mu$ m) cross-sectional images of plaque morphology, which allows optimizing stent placement and size and strut coverage (12). The results of a recent pilot study suggested that OCT can also be used to characterize the functional severity of the stenotic lesion via an image-based physiology assessment index called Virtual Flow Reserve (VFR). VFR is derived from a flow model based on three-dimensional lumen morphology of the OCT pullback images data to estimate the pre- and post-PCI coronary flow resistance. This technology has the potential to become an important stent planning tool that would be extremely useful to patients with complex lesions if it can be shown to correlate with computational FFR. The present VFR model utilizes a lumped parameter model for deriving the lesion associated physiology based on OCT pullback images. This image-based physiology assessment can not only evaluate the effect of lesion severity on coronary physiology while simultaneously evaluating the vascular/lesion

---

 Document 90465825 Virtual Flow Reserve Tech Report - Data on File at Abbott

*This confidential document is the property of Abbott and shall not be reproduced, distributed, disclosed or used without the express written consent of Abbott*

## Clinical Investigation Plan

condition but can provide the potential for conducting real-time stent planning due to the superior resolution that OCT images provided and the significantly short turnaround calculation time with minimal processing/calculation time.

### 2.0 CLINICAL INVESTIGATION OVERVIEW

#### 2.1 Clinical Investigation Objective

##### 2.1.1 Primary objective

The objective is to validate the diagnostic performance of VFR by comparing it against a reference standard, fractional flow reserve (FFR).

#### 2.2 Device(s) To Be Used in the Clinical Investigation

##### 2.2.1 Name of the Device(s)

The following devices will be used in this clinical investigation:

| Device name   | Model/Type       | Manufacturer        | Region/Country | Investigational or Market Released |
|---|------------------|---------------------|----------------|------------------------------------|
| ILUMIEN OPTIS OCT Imaging System                    | C408650          | Abbott Laboratories | Global         | Market Released                    |
| OPTIS Integrated OCT Imaging System                 | C408652 /C408653 | Abbott Laboratories | Global         | Market Released                    |
| OPTIS Mobile OCT Imaging System                     | C408661 /C408662 | Abbott Laboratories | Global         | Market Released                    |
| Dragonfly Duo Catheter                              | C408644 /C408643 | Abbott Laboratories | Global         | Market Released                    |
| Dragonfly OPTIS Catheter                            | C408645 /C408646 | Abbott Laboratories | Global         | Market Released                    |
| Dragonfly OpStar Catheter                           | 1014651          | Abbott Laboratories | Global         | Market Released                    |
| PressureWire™ X Guidewire Cable Connection (175 cm) | C12009           | Abbott Laboratories | Global         | Market Released                    |
| PressureWire™ X Guidewire Wireless (175 cm)         | C12059           | Abbott Laboratories | Global         | Market Released                    |
| PressureWire™ X Guidewire Wireless (300 cm)         | C12359           | Abbott Laboratories | Global         | Market Released                    |

*This confidential document is the property of Abbott and shall not be reproduced, distributed, disclosed or used without the express written consent of Abbott*

## Clinical Investigation Plan

Please refer to the Instructions for Use (IFU) for details of each respective system.

### 2.2.2 Indication for Use

Virtual Flow Reserve (VFR) is a physiologic index for diagnosing the functional significance of coronary stenoses based on the vascular morphology information obtained through OCT image pullback. VFR analysis is intended to support the functional evaluation of coronary artery disease and procedural scenario planning. The results of VFR are intended to be used by qualified clinicians in conjunction with the clinical history and symptoms of patients as well as other diagnostic tests according to clinician's professional judgment.

### 2.2.3 Description of the Device(s)

#### OPTIS System:

The ILUMIEN OPTIS™, OPTIS™ Integrated, and OPTIS™ Mobile systems with Dragonfly™ DUO or Dragonfly™ OPTIS™ or Dragonfly OpStar™ Imaging Catheter is intended for the imaging of coronary arteries and is indicated in patients who are candidates for transluminal interventional procedures.

The OPTIS™ Systems will further acquire radio frequency signal outputs from both a distal intracoronary pressure transducer and a proximal aortic pressure transducer to determine the physiological parameters, FFR and RFR. The physician may use the FFR and resting full-cycle ratio (RFR) parameter data, along with knowledge of patient history, medical expertise and clinical judgment to determine if therapeutic intervention is indicated.

#### Dragonfly:

The Dragonfly Duo, Dragonfly OPTIS or Dragonfly OpStar Imaging Catheter with the OCT Imaging System is intended for the imaging of coronary arteries and is indicated in patients who are candidates for transluminal interventional procedures. The Dragonfly Duo, Dragonfly OPTIS or Dragonfly OpStar Imaging Catheter is intended for use in vessels 2.0 to 3.5 mm in diameter. The Dragonfly Duo, Dragonfly OPTIS or Dragonfly OpStar Imaging Catheter is not intended for use in the left main coronary artery or in a target vessel which has undergone a previous bypass procedure.

#### PressureWire X:

PressureWire™ is designed to be used as a regular guidewire to direct a catheter through the blood vessel and to be used to measure intra-arterial pressures. The PressureWire devices consist of a 0.014" guidewire, a torque device, and a cable hookup, for PressureWire X (cable version), or wireless transmitter, for PressureWire X (wireless version). The guidewire has an integrated sensor chip element located 30 mm from the distal tip to enable measurements of physiological parameters such as pressure. Wireless PressureWire devices are all available in two different lengths, 175 cm and 300 cm. Each PressureWire X (wireless) guidewire is uniquely paired with a transmitter which sends data to a receiver using wireless technology.

PressureWire devices are used primarily for measurement of FFR and RFR. FFR is the ratio between the maximum flow distal to a stenosis and the normal maximum flow in the same vessel, calculated by

*This confidential document is the property of Abbott and shall not be reproduced, distributed, disclosed or used without the express written consent of Abbott*

## Clinical Investigation Plan

FFR = Pd/Pa where Pd is the pressure distal to the stenosis and Pa is the aortic pressure. While FFR is measured during hyperemia, RFR measures Pd and Pa over the entire cardiac cycle at rest (sampled at 100 Hz) and uses a moving average filter to determine the minimum value of the Pd/Pa ratio, which is then averaged over multiple cardiac cycles to obtain the resting index. In case of multiple sequential stenoses or diffuse lesions, RFR pullback pressure assessment can identify multiple lesions with functional significance.

The indications for PressureWire in all geographies can be found in the instructions for use (IFU) provided with the product or on the [eIFU.abbottvascular.com](http://eIFU.abbottvascular.com) website.

Please refer to the IFU for additional information regarding the device used in this clinical investigation.

### 2.2.4 Summary of Preclinical Studies

A summary of VFR theoretical backgrounds is provided in **Document 90465825 Virtual Flow Reserve Tech Report**

## 3.0 CLINICAL INVESTIGATION DESIGN

This study is a single-arm, prospective, multi-center study collecting OCT pullback images of lesions pre-PCI and (optional) post-PCI procedure, and the corresponding pressure tracings and physiology indices. No investigational device will be used in this study. VFR will be calculated offline using the OCT pullback images. Up to 30 centers in the US will enroll approximately 310 patients. There will be no clinical follow-up after completion of the PCI procedure. The expected duration of enrollment is approximately 15 months. The total duration of the clinical investigation is expected to be approximately 27 months.

### 3.1 Clinical Investigation Procedures Schedule

Subjects will be considered enrolled in this clinical investigation when all of the following criteria are met: Informed Consent Form (ICF) is signed, they meet all eligibility criteria and have undergone physiological indices measurement and OCT pullbacks. Enrolled subjects must follow all CIP requirements.

Data will be collected at baseline, during procedure, and post-procedure. There is no clinical follow-up in this study. The flowchart of the process is shown in **Figure 2** below.

[figure not shown]
---

Document 90465825 Virtual Flow Reserve Tech Report - Data on File at Abbott

*This confidential document is the property of Abbott and shall not be reproduced, distributed, disclosed or used without the express written consent of Abbott*

## Clinical Investigation Plan

Figure 2: Clinical Investigation Flow Chart

*This confidential document is the property of Abbott and shall not be reproduced, distributed, disclosed or used without the express written consent of Abbott*

[figure not shown]
## Clinical Investigation Plan

### 3.2 Measures Taken to Avoid and Minimize Bias

#### 3.2.1 Blinding and Unblinding

Investigational sites will directly upload and transfer the raw unidentified pullback images and pressure tracings to an independent core laboratory. The core laboratory will perform a quality check on OCT pullbacks and pressure tracings. Once the quality check is completed for every 50 patients, these OCT pullbacks will be transferred to Abbott personnel (Group 1) to analyze VFR (Figure 3). All Abbott personnel who are responsible for the calculation of VFR (Group 1) will be blinded to all physiology data (Pd/Pa, RFR, and FFR snapshots as well as RFR pullback). Abbott personnel responsible for performing the primary endpoint analysis (Group 2) will be blinded to the VFR data until all patients have been enrolled and all VFR data have been cleaned and generated. Additional data transfer detail is outlined in the data management plan (DMP) document.

Figure 3: Blinding/Unblinding Flowchart

#### 3.2.2 OCT and Physiology Core Laboratory

The clinical investigation will utilize an independent OCT and physiology core laboratory for the assessment and evaluation of all OCT pullbacks and pressure tracings required during the clinical investigation period. All clinical investigation-required OCT pullbacks and pressure tracings must be submitted to the core laboratories by uploading the assessments directly to the core laboratories' database.

Pressure tracings will also be reviewed for pressure drift and significant artifacts per the core laboratory's standard operational procedure. Reasons of rejection for each unacceptable pressure tracing will be documented by the core laboratory. All the remaining acceptable pressure tracings will be subsequently transferred to the sponsor.

*This confidential document is the property of Abbott and shall not be reproduced, distributed, disclosed or used without the express written consent of Abbott*

## Clinical Investigation Plan

To ensure timely feedback on the quality of OCT pullbacks and pressure tracings, as well as a balanced baseline FFR distribution in line with study assumptions, the core lab will send data quality and baseline FFR data to Abbott (group 2) for [REDACTED] enrolled subjects (**Figure 3**). Based on this information, Abbott may choose to work with the sites on improving data quality as well as rebalancing the FFR distributions via encouraging or capping enrollment in certain subgroup(s). If the enrollment cap is implemented, protocol deviation(s) will be given if the sites do not follow the capping criteria.

### 3.3 Suspension or Early Termination of the Clinical Investigation

While no formal statistical rule for early termination of the clinical investigation for insufficient effectiveness of the device under investigation is defined, the Sponsor reserves the right to discontinue the clinical investigation at any stage or reduce the follow-up period with suitable written notice to the investigator. Possible reason(s) may include, but are not limited to:

- An oversight committee (e.g., Steering Committee) makes a recommendation to stop or terminate the clinical investigation (such as higher frequency of anticipated adverse device effects)

Should the clinical investigation be discontinued by the Sponsor, subjects will be followed per routine hospital practice with device-related AEs reported to the Sponsor as per vigilance/commercial reporting requirements. The investigator shall provide a written statement to the IRB. All applicable clinical investigation documents shall be subject to the same retention policy as detailed in **Section 11.5** of the CIP.

A Principal Investigator, IRB or regulatory authority may suspend or prematurely terminate participation in the clinical investigation at the investigational site(s) for which they are responsible. The investigators will follow the requirements specified in the Clinical Trial Agreement.

If the Sponsor suspends or prematurely terminates the clinical investigation at an individual site in the interest of safety, the Sponsor will inform all other Principal Investigators.

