## 7.2 Device Relationship

Determination of whether there is a reasonable possibility that an investigational product or device under investigation caused or contributed to an AE is to be **determined by the Investigator** and recorded on the appropriate CRF form. Determination should be based on assessment of temporal relationships, evidence of alternative etiology, medical/biologic plausibility, and patient condition (pre-existing condition).

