### 10.9 Committees

#### 10.9.1 Steering Committee

The Steering Committee is responsible for overseeing the scientific and operational aspects of the clinical investigation. This committee will meet regularly to monitor subject enrollment, general data collection and non-compliance with the CIP at individual centers, to review operational issues that may arise and warrant a CIP amendment or other corrective action and to determine policy regarding any publications arising from data generated from the performance of the clinical investigation.

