### Ensuring strict adherence to the clinical investigation protocol

The clinical investigation will be carefully monitored by the Sponsor monitor (or designee) to ensure adherence to the Clinical Investigational Plan. Adverse events and device deficiencies will be reported to Abbott/designee and will be monitored internally for safety surveillance purposes.

*This confidential document is the property of Abbott and shall not be reproduced, distributed, disclosed or used without the express written consent of Abbott*

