## Clinical Investigation Plan

### 15.6 Risk to Benefit Rationale

The foreseeable rates of the anticipated adverse events associated with the procedure of FFR and OCT imaging systems are all below 10% (see **Appendix IV**). Moreover, as detailed in **Section 15.1**, evidence indicates that use of physiological measurements, such as VFR and FFR, in diagnosing the functional significance of coronary stenoses based on the lumen information obtained through OCT image pullback can potentially support the functional evaluation of coronary artery disease and procedural scenario planning can aid the decision-making of qualified clinicians, in conjunction with the clinical history and symptoms of patients as well as other diagnostic tests according to clinician's professional judgment. In turn, the following clinical benefits may be observed: (a) improved outcomes of PTCA (percutaneous transcutaneous coronary angioplasty), (b) reduced incidence of major adverse coronary events in patients being treated for complex CAD (coronary artery disease), (c) improved accuracy in the identification of hemodynamically relevant stenosis compared to use of angiography alone, and (d) reduced mortality and myocardial infarction compared to use of angiography alone.

*This confidential document is the property of Abbott and shall not be reproduced, distributed, disclosed or used without the express written consent of Abbott*

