#### **Adverse Device Effect (ADE):**

An adverse event related to the use of an investigational medical device.

This definition includes adverse events resulting from insufficient or inadequate instructions for use, deployment, implantation, installation, or operation, or any malfunction of the investigational medical device.

This definition includes any event resulting from the use error or from intentional misuse of the investigational medical device.

*This confidential document is the property of Abbott and shall not be reproduced, distributed, disclosed or used without the express written consent of Abbott*

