#### Pre-PCI Physiological Indices

1. Zero aortic transducer.
2. Flush and zero PressureWire™ outside the body.
3. Administer at least 100 µg of IC nitroglycerin.
4. Advance PressureWire to equalize position (guide disengaged).
5. Flush the guiding catheter to ensure appropriate aortic waveform (dicrotic notch).
6. Equalize PressureWire.
7. Remove any other coronary wires from within the target vessel.
8. Advance the PressureWire at least 10 mm distal to the most distal target lesion.
9. Document PressureWire position with cine documentation with contrast administration.
10. Flush the guiding catheter with saline.
11. Record the baseline blood pressure (with confirmation of distinct dicrotic notch with guide disengaged).
12. Capture Pd/Pa and RFR snapshots.
13. Induce maximal hyperemia with Adenosine per standard institutional practice (140 µg/kg/min IV or high dose 200 µg or 100 µg for the left or right coronary artery IC adenosine, respectively).
14. Record FFR.
15. Wait until hyperemia has worn off by confirming Pd/Pa has returned to the resting value.
  - a. 1 minute following IC administration
  - b. 3 minutes following IV administration
16. Record for RFR pullback (0.5mm/sec).
17. Check for pressure drift (i.e. range on 0.97-1.03 is accepted) and record the Pd/Pa snapshot value in FFR mode. If drift is present, physiology measurements are repeated after re-equalization at the aorto-ostial junction.
18. Remove PressureWire.
19. Upon completion of physiological measurement, record device lot and model numbers
20. Complete Adverse Event eCRF, if applicable (adverse device effects).

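### The protocol's adverse-event wording contradicts itself on what a device effect is, what sites record, and what rates are expected

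*Protocol*

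**What the plan says.** **Stopping (Protocol 3.3).** The sponsor may stop at any stage. One possible reason is listed, and the list is expressly open: an oversight committee, with the Steering Committee as the example, "makes a recommendation to stop or terminate the clinical investigation (such as higher frequency of anticipated adverse device effects".

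**Definition (Protocol Appendix II).** An adverse device effect (ADE) is "An adverse event related to the use of an investigational medical device". A serious ADE is an ADE with serious consequences, so it inherits the same condition. Section 3.0 states "No investigational device will be used in this study". All nine entries in the 2.2.1 device table are market released, and 11.6 says the same of the study as a whole.

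**Causality (Protocol 7.2).** The investigator judges "whether there is a reasonable possibility that an investigational product or device under investigation caused or contributed to an AE" and records the answer on the CRF.

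**Collection.** Protocol 7.3.1 requires all adverse events through the end of the procedure, and 7.1.1 Note 2 counts procedure-related events as AEs. In Appendix XI the physiology checklist ends with "Complete Adverse Event eCRF, if applicable (adverse device effects", in brackets. The pre-PCI and post-PCI OCT checklists end the same way. The PCI checklist instead has adverse events in the brackets.

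**Expected rates.** Protocol 15.6, citing Appendix IV, says: "The foreseeable rates of the anticipated adverse events associated with the procedure of FFR and OCT imaging systems are all below 10" percent. The highest frequency class in both Appendix IV tables is 0.5% or more, with no upper limit.

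**Reporting (SAP 3.2).** AEs are summarised by number of events and percentage of subjects. No split by seriousness or device relationship is specified.

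**The concern.** The one illustrated reason for a study-wide stop compares a count (ADEs) with an expectation (the anticipated frequency). The definition of the count conflicts with the device status of the study. The expectation is a class with no top. Anyone applying the example would first have to decide what the protocol meant.

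The collection prompt matters more in practice. Appendix XI is the step list used in the catheterization laboratory. A site that follows it literally could leave out events from hyperemia, contrast or the procedure itself at the physiology and OCT steps, because these are not device effects in the ordinary sense. SAP 3.2 would then under-count AEs at the steps the protocol requires. With up to 30 sites, different readings would also make the counts inconsistent between sites.

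**Working it through.** **1. Is the ADE category empty?** Set the texts side by side.

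- Condition in Appendix II: related to an investigational medical device.
- Protocol 3.0: no such device is used, and VFR is calculated offline.
- Protocol 2.2.1 and 11.6: only market-released devices.

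Taken literally, no event can qualify. Other text points to a different intent. Protocol 7.3.1 starts safety surveillance when the study device enters the vasculature, which can only be a wire or catheter. Section 15.2 discusses PressureWire and OCT risks under a heading that includes anticipated ADEs. Appendix XI applies ADE wording to both devices. The intended meaning can be recovered, but the definition contradicts it. The term study device is not itself defined.

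**2. Which prompt does a site see?** Appendix XI has four written AE prompts.

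| Step | Bracketed wording |
|---|---|
| Pre-PCI physiology | adverse device effects |
| Pre-PCI OCT | adverse device effects |
| PCI | adverse events |
| Post-PCI OCT (optional) | adverse device effects |

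Three of four are narrower than 7.3.1. Post-PCI physiology refers back to the pre-PCI steps and so repeats the narrow prompt. Appendix XI ends the protocol after OCT when no PCI follows, so for those subjects every prompt seen is the narrow one. Table B of Appendix IV itself anticipates events at the OCT step that come from contrast or drugs: an allergic reaction, and renal insufficiency or failure from contrast.

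**3. Can Appendix IV show rates all below 10%?** Row counts by class:

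| Class | Table A (FFR) | Table B (OCT) |
|---|---|---|
| 0.5% or more | 7 | 11 |
| 0.1% to under 0.5% | 10 | 1 |
| 0.001% to under 0.1% | 0 | 0 |
| under 0.001% | 4 | 3 |
| Total | 21 | 15 |

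Open-ended rows: 7 + 11 = 18 of 21 + 15 = 36, or 50%. For these rows the table gives a floor and no ceiling. The 10% figure cannot be reproduced from the appendix, which neither confirms nor contradicts it.

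**4. How wide is the ambiguity?** Accept the 10% from 15.6. Each of the 18 rows then has an expected rate somewhere from 0.5% to just under 10%, a 20-fold range (10 / 0.5 = 20). As an illustration only, take n = 310 and an assumed one-sided level of 0.025; the protocol sets no safety level. Find the smallest r with P(X ≥ r) ≤ 0.025, where X is binomial(310, p).

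| Assumed p | Expected (310 × p) | r | P(X ≥ r) |
|---|---|---|---|
| 0.5% | 1.55 | 5 | 0.0207 |
| 1% | 3.1 | 8 | 0.0137 |
| 2% | 6.2 | 12 | 0.0237 |
| 5% | 15.5 | 24 | 0.0238 |
| 10% | 31 | 43 | 0.0180 |

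For one unspecified event type, a count that stands out as higher could be anywhere from 5 to 43. This measures how little the stated class says. It is not a proposed threshold.

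**The case against.** Much of the case on the other side stands.

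A reader might infer that 3.3 is the only safety stop and that it cannot work. The documents do not support this. The list of reasons is open, and the committee and the ADE frequency are both examples. The sponsor's right to stop is unconditional. Section 3.3 also gives routes to investigators, IRBs and regulators, and refers to a sponsor stop at a single site for safety.

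A reader might infer that nobody reviews AEs, since 10.9.1 says of the Steering Committee: "This committee will meet regularly to monitor subject enrollment, general data collection and non-compliance with the CIP at individual centers". But 15.5 has AEs reported to the sponsor, where they "will be monitored internally for safety surveillance purposes", and the sponsor holds the right to stop. The committee also oversees scientific and operational aspects generally, and nothing denies it AE data. Its safety remit is a missing detail, not an error.

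A reader might turn the open class into a range of deaths that would count as anticipated. That applies a generic class floor, and a ceiling covering all event types, to one outcome. It also ignores that each death is an SAE, due to the sponsor within 3 calendar days, with onward IRB and regulatory reporting. Section 15.2 places likely incidence in the IFUs as well, and these may hold narrower rates.

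Appendix XI does not say that only device effects are recorded, and 7.3.1 is explicit that all AEs are. Event loss is therefore a risk, not a certainty. Nor can one say that the CRF lacks an item for procedure relationship, because the forms are under separate cover (Appendix V). SAP 3.5 allows additional analyses per the table mock-ups.

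What does not fall away is the conflict between the texts. Evidence of intent elsewhere does not repair the ADE definition, a general rule in 7.3.1 does not explain why three of four prompts are narrower, and 15.6 cites a table that cannot carry its figure.

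**Conclusion.** The point holds as a set of internal contradictions. Read literally, the ADE category is empty, although the protocol elsewhere applies the term to the wire and catheter. Three of the four AE prompts in Appendix XI are in tension with 7.3.1. Half of the Appendix IV rows (18 of 36) have no upper limit, so the 10% in 15.6 is unsupported by its own citation, though not shown to be false. The 3.3 example is ill-defined as a result.

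The consequences are limited. SAE reporting does not depend on the ADE term, so the under-recording risk falls mainly on non-serious, non-device events at the physiology and OCT steps. How many events that is cannot be estimated from the documents. The sensitivity and specificity analyses are untouched. The row counts rest on the tables as printed. The 5-to-43 range rests on the assumed 0.025 level and on taking 10% as the ceiling.

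**What to change.** - **Protocol Appendix II and 7.2:** define the study devices as the OCT systems, imaging catheters and PressureWires listed in 2.2.1. Tie ADE, serious ADE and the relationship question to them.
- **Protocol Appendix XI:** at the physiology and OCT steps, change the bracketed adverse device effects to adverse events, matching the PCI step and 7.3.1.
- **Protocol 15.6 and Appendix IV:** give the source for the 10% or correct it, and reconcile it with the open-ended class.
- **SAP 3.2:** tabulate AEs by seriousness and by the device relationship already recorded under 7.2.

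Once these agree, the example in 3.3 has a defined event and a stated comparator. No stopping threshold is proposed here; that is for the sponsor and its clinical advisers.

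The cost is minor rewording and one extra table split. No new CRF item is needed. The analysis of VFR against FFR does not change.
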